### **6.1 Inclusion Criteria**

1.  $\geq 18$  years of age

2. Histologic or cytologic confirmation of head & neck cancer (stage I-IV) or non-small cell lung cancer (stage II & III)
3. Undergoing definitive treatment with either radiation alone or in combination with systemic therapy
4. KPS $\geq$ 60
5. Willing to consent to participate
6. Normal cognition and willingness to complete fatigue and quality of life forms at each designated time point along with a patient observation form and pill diary
7. Life expectancy  $\geq$  3 months
8. Able to tolerate oral medication
9. Adequate organ function: laboratory values to be obtained within 90 days prior to registration or if not already performed, after subject consenting
  - a. Hematology: Absolute neutrophil count (ANC)  $\geq$ 1500/ $\mu$ L, Hemoglobin (Hgb)  $\geq$ 9.0

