## 6.2 Exclusion Criteria

1. Hypersensitivity to dexamethasone or corticosteroids or Equal sugar substitute
2. Corticosteroid within the past 30 days prior to registration on this study for greater than one week duration
3. Planned Stereotactic Body Radiation Therapy (SBRT)
4. Active psychosis
5. Current pregnancy
6. Active peptic ulcer disease or evidence of gastrointestinal bleed
7. Current active tuberculosis or systemic fungal infection
8. Previous diagnosis of diabetes mellitus
9. Acute febrile illness
10. Human immunodeficiency virus or acquired immunodeficiency syndrome
11. Major surgery within two weeks of study registration of which the patient has not recovered
12. Psychostimulant use in the past 30 days prior to registration
13. History of phenylketonuria (PKU)
14. Allergy to sugar substitute.

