Subjects will be seen once per week per standard of care for on-treatment visits. Weight, BP and evaluation of side effects (including mucositis evaluation) will be performed. FACIT-F 13-item fatigue subscale and FACIT-F 27-item total questionnaires will be completed by subjects during screening and on RT days 5 [ $\pm 2$  days], 10 [ $\pm 2$  days], 15 (day prior to IP start) [ $\pm 2$  days], 20 [ $\pm 2$  days], 25 [ $\pm 2$  days], 26 [ $\pm 2$  days] and 30 (or last day of RT if course extended) [ $\pm 2$  days] along with 30 day post RT follow-up [ $\pm 7$  days] and 60 day post RT follow-up [ $\pm 7$  days] to assess fatigue and QoL. If a subject discontinues IP early for any reason they will still complete FACIT surveys on RT day 26 [ $\pm 2$  days] so they can be included in an intention to treat analysis. Furthermore, if a patient has their RT extended, they will complete FACIT surveys on their last RT day rather than RT day 30.

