**9.6 Early treatment termination**

Subjects that terminate IP prior to the completion of the 14 day course will still be seen as per the study schedule and will complete FACIT surveys on RT day 25, 30 and the last day of RT if they receive more than 30 treatments [ $\pm 2$  RT days] so they can be included in an intention to treat analysis. For patients that have difficulty with transportation or keeping scheduled appointments, one of these follow-ups may be done over the phone. No vitals will be obtained, however, they will be asked the questions from the FACIT survey, as well as asked about any adverse events they may be experiencing.

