## 16. STATISITICAL CONSIDERATIONS

Statistical analysis will be performed in collaboration with [name], the Director of the University of Arizona Cancer Center Biometry Shared Service. The primary outcome is the change in the fatigue score between radiation days 15 (day prior to IP initiation) and 26 (day after IP completion) in the dexamethasone versus placebo patients as measured by the Functional Assessment of Chronic Illness-Fatigue (FACIT-F) 13-item fatigue subscale. Secondary endpoints include the QoL score as measured by the FACIT-F 40-item total score, and the total days and cause of treatment interruption. Randomization will be stratified by tumor location and treatment type (radiation alone versus radiation plus systemic therapy). Analysis of the continuous endpoints (change in FACIT-F fatigue subscale and change in FACIT-F total score) will be performed using a two-sample independent t test comparing the dexamethasone versus placebo patients. Analysis of the total days of treatment interruption will be performed using a Wilcoxon Rank Sum Test, since the number of days may not be normally distributed. Alternatively, the proportion of patients with any treatment interruptions will be compared using a Fisher's Exact Test.

The sample size of 40 patients per group was chosen based on the previous study of Yennurajalingam et al. in advanced cancer patients with at least three cancer-related fatigue symptoms. They observed a mean improvement in the FACIT-F fatigue score of 9.0 (standard deviation = 10.30) in the dexamethasone treated group versus a mean improvement of 3.1 (standard deviation = 9.59) in the placebo group. We chose a one-sided statistical test (at the alpha = 0.05 level) as dexamethasone will only be recommended in our patient population if it improves cancer-related fatigue. Based on these considerations, 36 patients per group will provide 80% statistical power. We rounded the necessary sample size up to 40 patients to allow for the possibility of up to a 10% drop-out of patients from their radiation therapy between days 16 and 26.

Exploratory analyses will profile the change in the FACIT-F fatigue subscale and FACIT-F total score across the entire radiation therapy course (measured at baseline screening, on RT days 5, 10, 15, 20, 25, 26, and 30, and 60 day follow-

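### No rule gives a primary fatigue score to patients whose radiation ends before RT day 26, so the primary comparison is limited to those who stay on radiation

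*Combined protocol and SAP*

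**What the plan says.** Section 16 defines the primary outcome as the "change in the fatigue score between radiation days 15 (day prior to IP initiation) and 26 (day after IP completion", and tests it with a "two-sample independent t test comparing the dexamethasone versus placebo patients". It gives no rule for a missing RT day 26 score. The sample size is 36 per group for 80% power, raised to 40 "to allow for the possibility of up to a 10% drop-out of patients from their radiation therapy between days 16 and 26".

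Four places keep surveying patients after treatment changes, and all four concern stopping the study drug:

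- Section 7.1: "If a subject discontinues IP early for any reason they will still complete FACIT surveys on RT day 26", so that they can enter an intention-to-treat analysis.
- Section 8.2: patients taken off study drug for raised glucose continue weekly surveys during RT and at 30 and 60 days after it.
- Section 9.6: patients who end study drug early are surveyed on RT days 25 and 30 and, if they have more than 30 treatments, on the last RT day. For those with transport or appointment difficulties, "one of these follow-ups may be done over the phone".
- Section 16: the questionnaire continues after study drug is terminated.

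On eligibility, Section 6.1 asks for patients "Undergoing definitive treatment with either radiation alone or in combination with systemic therapy". Section 6.2 excludes planned SBRT and sets no other limit on the radiation schedule. Section 2.4 calls a six-to-seven-week course typical; it is not a criterion.

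**The concern.** The endpoint is counted in radiation days. A patient who leaves radiation for good between RT days 16 and 26 may never reach the primary assessment, and the provisions for patients who stop study drug do not help, because their on-treatment dates are also tied to RT. The sample-size paragraph then provides for such patients only as drop-outs.

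This matters because leaving radiation happens after randomisation. Section 4.1 postulates that fatigue may affect the ability to complete therapy uninterrupted, Section 4.1 also hypothesises that the steroid will affect interruption, and interruption is a secondary endpoint. If permanent stopping follows the same pattern, the missing scores depend on fatigue and on arm. Enrolling more patients restores power but leaves that selection in place. Sections 7.1 and 9.6 say an intention-to-treat analysis is wanted, so the gap runs against the protocol's own aim.

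**Working it through.** **1. The plan's own sample size.** Inputs from Section 16: mean improvements 9.0 (SD 10.30) and 3.1 (SD 9.59), one-sided alpha 0.05, power 80%.

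- Difference = 9.0 − 3.1 = 5.9. Pooled SD = √((10.30² + 9.59²)/2) = 9.951.
- n per group = 2 × (1.645 + 0.842)² × 9.951² / 5.9² = 35.2, rounded up to 36.
- With 10% loss: 36 / 0.90 = 40.
- Power by noncentral t (noncentrality = 5.9 / (9.951 × √(2/n)), 2n − 2 degrees of freedom): 80.1% at 36 per group.

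Both stated figures reproduce. The arithmetic is not at fault.

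**2. Who lacks a primary score.** The RT day 26 survey has a window of plus or minus 2 days, so a course reaching RT day 24 can supply it. Below about RT day 24 there is no qualifying survey. Section 26 marks FACIT-F on the last day of RT and at the 30 and 60 day visits, but no section lets these stand in for the primary score.

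**3. Bias from analysing stayers only.** Let p be the share leaving radiation in an arm and k the number of points by which leavers' change is worse than stayers'. The full-arm mean is (1 − p)·m + p·(m − k) = m − p·k, so the stayers' mean m exceeds it by p·k. With the same k in both arms, the bias in the difference (dexamethasone minus placebo) is (p_dex − p_plac) × k. The documents give neither p by arm nor k; the values below are assumptions.

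| Placebo leaving | Dexamethasone leaving | k = 5 | k = 10 | k = 15 |
|---|---|---|---|---|
| 10% | 5% | −0.25 | −0.50 | −0.75 |
| 15% | 5% | −0.50 | −1.00 | −1.50 |
| 10% | 10% | 0 | 0 | 0 |

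Against 5.9, the non-zero entries run from 0.25/5.9 = 4% to 1.5/5.9 = 25%. The sign reverses if dexamethasone patients leave more often.

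**4. What including leavers does to power.** Take all 40 per group as analysed, with SD unchanged:

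- Leavers have the full effect (5.9): 83.7%.
- 5% have no drug effect (5.9 × 0.95 = 5.605): 80.3%.
- 10% have no drug effect (5.9 × 0.90 = 5.31): 76.4%.

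**5. Calendar equivalent of RT day 26.** RT runs Monday to Friday (Section 2.4) and study drug starts on RT day 16. Ten RT days later is 14 calendar days later if there is no break, so RT day 26 falls on day 15 counted from the first dose. That is the day after a 14-day course ends, as Section 16 intends.

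**6. The survey schedules side by side.** Section 7.1 lists RT days 25, 26 and 30, with the last RT day replacing day 30 only if the course is extended. Section 9.6 lists days 25, 30 and the last day beyond 30 treatments, without day 26. The FACIT-F row in Section 26 has marks at RT days 25 and 30 and the last day, and none at day 26.

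**The case against.** Several stronger readings are tempting, and the documents do not support them.

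- *That no survey is due once radiation ends.* Section 26 has a separate last-day column with a FACIT-F mark, and marks both follow-up visits. What is missing is a rule linking any of these to the primary score. Some notes in that table (the double asterisk, 11 and 12) and the calendar listed as 30.1 could not be read in the available text, so the claim cannot be wider than this.
- *That the plan states these patients are excluded.* It does not. Exclusion is inferred from the drop-out allowance and from a t test on change scores with no missing-data rule. Section 15 also allows continued collection of endpoint data to be discussed, although for patients who stop study drug.
- *That the protocol says fatigue makes patients abandon radiation.* Section 4.1 speaks of interruption, and its opening discussion only postulates the link. A patient who pauses and resumes still reaches RT day 26. Only permanent stopping loses the score, and the sole figure for it is up to 10%.
- *That the fix buys power.* Step 4 shows it may lower it.
- *That many short-course patients would be enrolled.* Nothing suggests so. The typical course is six to seven weeks and SBRT is excluded, so the number is unknown and probably small.

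It also stands that the bias inputs are assumed. The scenario with more placebo leavers biases against the drug, and equal leaving with equal deficits gives no bias. A calendar date for leavers alone leaves mixed timing: Section 8.3 continues study drug through RT breaks, so a patient with a break is assessed later relative to dosing.

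**Conclusion.** The concern holds in a limited form. The primary score depends on reaching about RT day 24, the intention-to-treat provisions address stopping study drug rather than stopping radiation, and no other survey may replace the missing score. The analysis as written therefore conditions on staying on radiation. Under the assumed leaving rates and deficits, the distortion is 0.25 to 1.5 points in either direction, depending on which arm leaves more; it is zero if rates and deficits match. That is modest beside 5.9, but it cannot be checked if the scores are never collected. The reason to act is validity. The missing minimum course length is a secondary gap of unknown and probably small effect.

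**What to change.** - **Sections 7.1, 9.6 and 16:** state that a patient whose radiation ends before RT day 26 completes the FACIT-F on the calendar day after the planned 14-day study-drug period would end (day 15 from first dose), in clinic or by phone, and is included in the primary analysis by randomised arm. Reserve the term drop-out for patients with no questionnaire. This gives no date for a randomised patient who never takes a first dose, and the allowance for days 16 to 26 does not cover that patient either, so Section 16 should say how such patients are handled.
- **Section 6.1:** state that the planned course must reach the primary assessment day, RT day 26. A 30-day minimum would go further than needed, since it would also exclude courses of 24 to 29 RT days, which can supply the score within the window.
- **Sections 7.1, 9.6 and 26:** reconcile the survey days (RT day 25, RT day 26, last day of RT).

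Cost: protocol wording, one extra questionnaire in up to about 8 patients (10% of 80), a probably small loss of accrual, and possible dilution of the estimated effect if leavers gain nothing from the drug.

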#### 4.2 Investigational Product: Decadron (dexamethasone)

Corticosteroids are structurally similar to endogenous cortisol and act on target cells by regulating the transcription of target genes. Arguably their most clinically relevant side

effects involve the endocrine system, in particular adrenal suppression and hyperglycemia.

Adrenal suppression occurs in a dose and duration dependent manner, and may cause an inadequate stress response if major illness concurrently occurs. Patients receiving any corticosteroid dose for less than three weeks duration are considered unlikely to develop suppression and may stop treatment without a taper. This study will attempt to treat radiation fatigue with a 14 day non-tapered course of dexamethasone as previously published.

Hyperglycemia with corticosteroids occurs because of decreased insulin sensitivity, increased gluconeogenesis, and inhibition of insulin secretion. A typical 10-20% increase in blood glucose has been reported with up to one fifth developing steroid diabetes. No official recommendation exists on monitoring blood glucose during acute treatment. The only available guide is in the setting of chronic post-transplant therapy, which recommends screening fasting plasma glucose (FPG) levels once a week during the first four weeks.

Some have argued that FPG levels may actually be a poor marker during corticosteroid treatment because these drugs influence post-prandial levels most significantly and often do not affect fasting levels. Trence recommends checking weekly random plasma glucose (RPG) levels during corticosteroid treatment with a goal below 180 mg/dL. Similarly, Lansang and Hustak endorse RPG with a level of  $\geq 200$  and classic symptoms of diabetes for detecting glucocorticoid-induced diabetes. This cutoff is taken directly from diabetes guidelines and is an official criterion for the diagnosis of diabetes.

As an added safety measure this study will monitor RPG levels during dexamethasone treatment since they are influenced more than FPG and we wish to avoid fasting in our patient population. Encouraging fasting in patients who commonly experience anorexia and weight loss from both disease and RT would promote suboptimal care.

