up) separately for the dexamethasone versus placebo treated patients. Descriptive statistics (mean, medians, standard deviations) will be computed separately for each treatment group at each time point.

The primary safety endpoint is random plasma glucose levels measured on radiation therapy day 15, 20 and 25. Treatment will be terminated in patients if the RPG  $\geq$  250 mg/dL. The FACIT-F questionnaire will continue to be administered per study protocol even if dexamethasone or placebo treatment is terminated. The proportion of patients with treatment terminations will be compared between the two groups using a Fisher's Exact Test. Adverse events will be summarized using CTCAE criteria for each treatment group separately.

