## **17. ANALYSIS**

### **17.1 Safety Analysis**

The first safety analysis will be conducted when 20 subjects have completed study treatment. Additional analysis will be done every 20 patients. A brief report will be generated describing any adverse events experienced and number of subjects that were unable to complete IP treatment.

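### The primary safety endpoint, random plasma glucose level, has no planned analysis; the only safety test compares treatment terminations, which are largely insensitive to the glucose rise the protocol calls typical

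*Combined protocol and SAP*

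**What the plan says.** Section 16 names the endpoint: "The primary safety endpoint is random plasma glucose levels measured on radiation therapy day 15, 20 and 25". It then gives the 250 mg/dL stopping threshold and moves to the comparison: "The proportion of patients with treatment terminations will be compared between the two groups using a Fisher's Exact Test". No alpha, sidedness, expected rate or power is attached to that test.

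The remaining safety output is descriptive. Section 16 adds: "Adverse events will be summarized using CTCAE criteria for each treatment group separately". Section 17.1 covers the periodic review: "A brief report will be generated describing any adverse events experienced and number of subjects that were unable to complete IP treatment". Neither mentions glucose level.

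The other methods in Section 16 are assigned elsewhere. The t test is for the two FACIT-F changes and the Wilcoxon test is for days of interruption. The sentence on means, medians and standard deviations closes the paragraph on exploratory FACIT-F profiles.

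The only figures on the size of a glucose effect are in Section 4.2: "A typical 10-20% increase in blood glucose has been reported with up to one fifth developing steroid diabetes".

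**The concern.** The endpoint is a level on a continuous scale, and the test is on a different variable. Termination differs from glucose level in two ways.

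- It reduces glucose to whether a reading reached 250 mg/dL, in patients with no previous diagnosis of diabetes (Section 6.2). A shift below that threshold leaves no trace in the test.
- It is not confined to glucose. Section 8.3 also allows stopping for unacceptable toxicity, Section 15 allows patients to stop by choice, and Section 8.2 allows a stop and restart around a long radiation break. The plan does not say which of these count.

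Section 4.2 ranks hyperglycemia among the most clinically relevant side effects of corticosteroids. Followed as written, the trial would collect glucose at three visits and never estimate the difference between arms. With the analysis left open, the time point and summary could also be chosen after the data are seen.

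**Working it through.** **1. The plan's own sample size.** The inputs are in Section 16: "mean improvement in the FACIT-F fatigue score of 9.0 (standard deviation = 10.30) in the dexamethasone treated group", "mean improvement of 3.1 (standard deviation = 9.59) in the placebo group", and "We chose a one-sided statistical test (at the alpha = 0.05 level".

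- Pooled SD = √[(10.30² + 9.59²)/2] = 9.951; difference = 9.0 − 3.1 = 5.9.
- n per arm = 2 × (1.645 + 0.842)² × 9.951² / 5.9² = 35.2, so 36. Power at 36 by the noncentral t is 80.1%.
- 36 / 0.90 = 40.

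The stated 36 and 40 reproduce. They concern fatigue only; no corresponding calculation exists for safety.

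**2. Where the expected rise falls relative to the threshold.** Assume a mean of 110 mg/dL without dexamethasone (the documents give none). A 10% rise gives 110 × 1.10 = 121 mg/dL and a 20% rise gives 110 × 1.20 = 132 mg/dL. These leave 250 − 121 = 129 and 250 − 132 = 118 mg/dL to the threshold. With an assumed SD of 50 mg/dL, that is 129/50 = 2.6 and 118/50 = 2.4 SDs; with a smaller SD it is further.

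**3. Power of Fisher's exact test on terminations.** Power is the sum, over all pairs of counts with p ≤ 0.05, of the product of the two binomial probabilities. All rates are assumed, and so is the two-sided 0.05 level; 40 per arm.

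| Dexamethasone vs placebo | Two-sided | One-sided |
|---|---|---|
| 5% vs 0% | 1% | 5% |
| 10% vs 0% | 21% | 37% |
| 20% vs 5% | 41% | 54% |
| 20% vs 0% | 84% | 92% |

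With no terminations on placebo, 5/40 on dexamethasone gives two-sided p = 0.055 and 6/40 gives p = 0.026.

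**4. Power of a direct comparison of glucose.** Two-sample t test, two-sided 0.05, 40 per arm, noncentrality = difference / (SD × √(2/40)). The differences are 10% and 20% of 110, that is 11 and 22 mg/dL. SDs are assumed.

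| SD (mg/dL) | 11 mg/dL | 22 mg/dL |
|---|---|---|
| 20 | 68% | over 99% |
| 30 | 37% | 90% |
| 40 | 23% | 68% |
| 50 | 16% | 49% |

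No gain from baseline adjustment is included.

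**5. Both tests on one distribution.** Steps 3 and 4 rest on unrelated assumptions, so they cannot be compared directly. To link them, assume lognormal glucose with placebo mean 110 mg/dL, coefficient of variation (CV) 20-50%, a 10-20% rise on dexamethasone, and termination if a reading is at or above 250.

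- The most favourable case for Fisher is CV 50% with a 20% rise. The chance that a single reading reaches 250 is then 5.6% vs 2.4%, and two-sided power is about 1%. If either of two independent readings can trigger a stop, the rates become 1 − (1 − 0.056)² = 10.9% and 1 − (1 − 0.024)² = 4.8%, and power is about 6%.
- A t test on log glucose at a single visit has about 15% power (CV 50%, 10% rise) to 98% (CV 20%, 20% rise).

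This step counts glucose-triggered stops only.

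**The case against.** The strongest reply is that Section 16 does carry glucose into a between-arm comparison. It moves from the endpoint to the 250 mg/dL threshold, which Section 7.1 ties to a modified Grade 3 hyperglycemia, and then to terminations. Hyperglycemia recorded as an adverse event would also appear in the CTCAE summary by arm. This stands in part: severe hyperglycemia is not ignored. It does not supply an analysis of glucose level, and the tested event can include stops unrelated to glucose.

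Three stronger readings are tempting, and the documents do not support them.

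- A reader might infer that the Fisher test has almost no power whatever happens. That holds only if terminations are about 10% or less on dexamethasone. At 20% vs 0% the power is 84%. The one-fifth figure in Section 4.2 is an upper bound for steroid diabetes, a different event, so it neither establishes nor excludes such a rate.
- A reader might infer that a non-significant result will be presented as evidence of safety. No safety claim or non-inferiority conclusion is tied to the test, so this is speculation.
- A reader might call it an error to list day 15 among the endpoint days. Sections 7.1 and 16 make clear that it precedes study drug, and a baseline is needed. What is missing is only a statement that it serves as one.

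The reply can also note that a direct comparison is not always well powered. That is correct: 16% for 11 mg/dL at SD 50. Fingerstick and laboratory values may be mixed (Section 7.1), and permitted pre-chemotherapy steroids (Section 7.4) may add variability. This argues for reporting an interval; it does not argue against estimating the difference.

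**Conclusion.** The concern holds in this form: the declared primary safety endpoint has no analysis, and the one safety test uses a coarser, mixed-cause variable that is largely insensitive to the rise the protocol describes as typical. The first part follows from the text alone. The second rests on an assumed mean of 110 mg/dL. With both tests tied to one assumed lognormal distribution, Fisher's test on glucose-triggered stops has about 1% power at most on a single reading (about 6% if two independent readings count), against about 15-98% for a direct comparison.

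The power of the termination test as planned cannot be fixed from the documents, because they give no termination rate, alpha or sidedness for it. The efficacy sample size is unaffected.

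**What to change.** Add to Section 16:

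- **Main analysis.** Compare glucose on RT days 20 and 25 between arms in a repeated-measures model adjusted for day-15 glucose and the stratification factors. Include all randomised patients with a value, whether or not study drug was stopped. Report the difference with a 95% CI, and summarise glucose by arm and visit.
- **Sensitivity analysis.** Use the highest on-drug value, or day 20 alone, because patients stopped for high glucose may be off drug by day 25. State how on-drug readings are identified: with the ±2-day window, a day-25 reading can fall after the 14-day course has ended.
- **Terminations.** Keep them as supporting evidence. Define which stops count, separate glucose-triggered stops from others, and report the rate difference with a CI.
- **Test settings.** State alpha and sidedness for every safety comparison.

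The cost is one extra model on readings that Sections 7.1 and 26 already schedule. It needs no new visits and no change to any clinical rule.
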